9.5 Follow up visits – One month and three months (mechanistic sub-group only)

If a participant has agreed to take part in the mechanistic sub-group, visits to their local research site will be arranged by the site at one and three months from the date the participant's BCG was administered for those in the intervention arm or from the date of randomisation for those in the control arm. Site staff will take additional blood samples from participants at these visits. During the three-month visit, questionnaires will be completed as for all other patients and DBS test performed. The DBS test will be sent to the main laboratory based at the QE hospital.

Data point to be collected:

- Venepuncture
- DBS
- Exacerbations since baseline
- Hospitalisations
- CAT test

9.6 Three month follow up visit (participants not taking part in the mechanistic sub-group)

Participants will be sent a link via email or SMS text message to access and complete their three month follow up questionnaire at home (paper copies can be posted if requested). This is sent to the participant automatically by the trial EDC system. Participants will also complete a DBS test at home and post the sample to the main laboratory based at the QE hospital. If a participant does not complete the questionnaire online after being sent the link three times on days 2, 3 and 5 from the missed due date, the trial team will send the questionnaire via post (paper) to the participant 7 days from the missed due date. The participant will be asked to complete and return the questionnaire to the trial team at BCTU, in the format it was received. If no response is received/completed after the attempts have been made, this data will be considered missing for this follow up time point.

Data point to be collected:

- DBS
- Exacerbations since baseline
- Hospitalisations
- CAT test

9.7 Twelve month follow up visit

Participants will be contacted by the research site to set up the twelve month follow up visit which will take place at the research site. Once the follow-up visit date/time is confirmed, the participant will be notified, i.e. verbally, appointment card, SMS text, email or letter. At the twelve month follow up visit, site staff will complete the twelve months follow up form with the participant and will perform a DBS test.

Data point to be collected:

- DBS
- Hospitalisations in the last 12 months
- CAT test
- Medical history over last 12 months
- Vaccination in the last 2 months
- COPD exacerbations over last 9 months
- Concomitant medications
- Prescriptions over the last 12 months
- Steroid use
- Smoking status

If a participant is unable to be contacted to arrange a twelve month follow up visit after three attempts, the site will send a letter or email to the participant. This letter/ email will remind the participant that their twelve month follow up is due and ask them to contact the research site to arrange their follow-up visit.

If the participant makes no contact, after approximately 14 days of last contact attempt, the trial team will send a twelve month follow up questionnaire out to the participant. This will be sent either by post (paper) or email (with online link to the questionnaire). The participant will be asked to complete and return the questionnaire to the trial team at BCTU, in the format it was received. If no response is received within 31 days of the twelve month follow up due date, this participant will be considered lost to follow-up and the data will be considered missing for this follow up time point.

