1.2.4 Justification of choice of primary outcome(s)

AECOPD are a significant burden to both the individual and the healthcare system and are not adequately controlled by existing therapies. Exacerbation reduction is also important to patients.

The primary outcome is moderate to severe AECOPD rate up to 12 months follow up. This is defined by healthcare utilisation (taking additional antibiotics and/or steroids, as recorded in the medical record, including prescription data), although we will collect symptom and treatment data from participants to infer if the event was infective. This will include all major and minor Anthonisen criteria (35), as well as whether antibiotics, steroids or antipyretics were taken.

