Our calculation has also required us to estimate the mean number of exacerbations pp/year in the control group. Again, based on a similar population studied in the TWICS trial (50), we will assume an overall mean exacerbation rate of 2.25 pp/year in the control arm (no vaccine). As noted in the 'Justification for design' section, a 20% relative reduction in the mean exacerbation rate pp/year equates to the likely MCID, is similar to other widely used therapies considered clinically meaningful to use in frequent exacerbators, and thus is an appropriate effect size upon which to base the power calculation. This reduction corresponds to an absolute decrease of 0.45 in the mean exacerbation rate pp/year from 2.25 in the control arm to 1.8 in the BCG arm. To detect this difference, comparing two negative binomial rates using the sample size formulae in (55), with 90% power, and a type 1 error rate of 5% (i.e. α =0.05), requires 361 participants per group to be randomised, or 722 participants in total. Assuming a loss to follow-up rate of 10% over a twelve-month follow-up period (see retention rate section), the study requires 402 per group to be randomised or 804 participants in total.

To allow for some uncertainty around our estimates, we have explored through sensitivity sample size calculations the impact of changing the parameters. Our proposed sample size is still likely to provide adequate power even if our estimates are not quite as expected. For example, for negative binomial dispersion parameters ranging from 0.65 to 0.3, and for mean exacerbation rates in the control arm ranging from 1.42 to 2.5, a sample size of 804 participants provides between 80% and 92% power to detect relative reductions of 20% in the mean exacerbation rate pp/year.

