14.2 Analysis outcome

A separate Statistical Analysis Plan will be produced and will provide a more comprehensive description of the planned statistical analyses. A brief outline of the planned analyses is given below. The primary comparison groups will be composed of those randomised to BCG vaccine versus those randomised to the control arm. In the first instance, all analyses will be based on the intention to treat principle, i.e., all participants will be analysed in the intervention group to which they were

randomised irrespective of adherence to randomised intervention or protocol deviations. For all outcomes, appropriate summary statistics and differences between groups, e.g., incidence rate ratios, mean differences, relative risks, absolute differences will be presented, with 95% confidence intervals and p-values from two-sided tests also provided. Where possible intervention effects will be adjusted for the minimisation variables listed in Section ENROLMENT and RANDOMISATION , and baseline values (where appropriate and available). No adjustment for multiple comparisons will be made.

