14.2.1 Primary estimand

The primary estimand is the rate of moderate to severe acute exacerbations of AECOPD in adults with a primary clinical diagnosis of COPD and will be measured as the rate per person per year. The estimand will follow the principal stratum strategy and those who will be randomised and then receive a positive or indeterminate result in their IGRA test will be excluded from all analyses.

The primary estimand can be summarised as follows:

Population: Adults with a primary clinical diagnosis of COPD and a negative IGRA test, ≥2 AECOPD in the last 12 months, who have not been Immunosuppressed and have not received >20mg prednisolone per day for >14 days in the last 3 months, have not previously experienced of allergic reaction to vaccine and are not pregnant, if they are female.

Treatment Conditions: BCG vaccine compared to no vaccine (see Section 7.1 for details on the intervention)

Outcome: Rate per person per year of moderate to severe acute exacerbations of AECOPD

Time: 12 months after randomisation in the no vaccine group and 12 months after receiving the BCG vaccine in the BCG group

Summary Measure: Adjusted incidence rate ratio and 95% confidence interval

Intercurrent Events and Strategies: The intercurrent events are: positive or indeterminate IGRA test; treatment non-receivers (those who randomised to receive but did not receive the BCG vaccine for any reason); withdraw consent for providing follow up data or lost to follow up; and death. All intercurrent events apart the first one (i.e. tested positive in their IGRA test) will be dealt with using the treatment policy strategy for the primary estimand as we want to evaluate the treatment effect as it would occur in normal practice. The intercurrent event, positive or indeterminate IGRA test will be dealt with using the principal stratum strategy because we are interested in the treatment effect in the principal stratum in which the intercurrent event would not occur.

Other strategies evaluating different estimands will be discussed in further detail in the SAP.

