14.2.5 Missing data and sensitivity analyses

Every attempt will be made to collect full data to the end of the study on all study participants; it is thus anticipated that missing data will be minimal. Participants will be included in the primary analysis up to the time point they were last followed up. If no primary outcome data will be collected for a participant, they will not be included in the primary analysis in the first instance. This presents a risk of bias, and sensitivity analyses will be undertaken to assess the possible impact of the risk. This will consist of simulating the missing responses using a multiple imputation approach. Parameters used to simulate the missing responses will include the minimisation variables, intervention group, exposure time (person-years), and, if applicable, previous response at each time point. Full details will be included in the Statistical Analysis Plan.

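### The primary outcome comes from the medical record, but participants who do not respond are declared missing with no required record review, and censoring them does not deliver the stated treatment-policy strategy

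*Protocol*

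**What the plan says.** - **Outcome source.** Sections 1.2.4 and 8.2.1 define a moderate event by treatment use: "taking additional antibiotics and/or steroids, as recorded in the medical record, including prescription data". Severe events add hospitalisation. The blinded adjudication committee decides.
- **Non-response.** At 3 months (section 9.6), after the online reminders and a posted form, "this data will be considered missing for this follow up time point". At 12 months (section 9.7), after further contact attempts and a posted or emailed form, "this participant will be considered lost to follow-up and the data will be considered missing for this follow up time point".
- **Routine-data route.** Section 9.9 allows data from standard clinic visits or central NHS bodies for participants who decline trial follow-up. It describes this only for people who actively change their level of participation.
- **Recall periods.** The 3-month contact asks for exacerbations from baseline. The 12-month visit asks for "COPD exacerbations over last 9 months", but for prescriptions and hospitalisations over 12 months.
- **Estimand.** Section 14.2.1 lists non-receipt of vaccine, consent withdrawal or loss to follow-up, and death as intercurrent events that "will be dealt with using the treatment policy strategy for the primary estimand".
- **Analysis.** Section 14.2.5: "Participants will be included in the primary analysis up to the time point they were last followed up". Participants with no primary outcome data are left out in the first instance, with multiple imputation as a sensitivity analysis.

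**The concern.** A participant who stops replying has refused nothing, and the prescriptions and discharge letters that define the primary outcome are still in the record. As written, such a participant gets less follow-up than one who tells the site that trial visits are no longer wanted. In an open-label trial, willingness to respond can differ by arm, so primary-outcome data that could have been retrieved may be dropped unevenly.

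The estimand has the same weakness. Treatment policy uses outcomes observed after the intercurrent event. Loss to follow-up and refusal of data collection mean that no such outcomes are available: that is missing data, not an event a strategy can absorb. After death there is no outcome to collect. Censoring at last follow-up replaces the stated strategy with an assumption that loss is non-informative, and section 14.2.1 does not say so.

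**Working it through.** **1. Planned sample size.** Inputs from section 14.1: rates 2.25 and 1.80 per year, k = 0.36, 90% power, alpha 0.05. Section 14.2 makes the test two-sided ("with 95% confidence intervals and p-values from two-sided tests also provided"). With one year of exposure:

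- V1 = 1/2.25 + 1/1.80 + 2 × 0.36 = 1.72; (ln 0.8)² = 0.0498.
- Unpooled variance: n = (1.960 + 1.282)² × 1.72 / 0.0498 ≈ 363. Null variance at the average rate: 361.4. The stated 361 per group reproduces.
- 361 / 0.9 = 401.1, so 402 per group and 804 in total, as stated.

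**2. Power.** With each participant contributing information rt/(1 + krt):

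| Situation at 402 per group | Power |
|---|---|
| All followed for 12 months | 92.7% |
| 10% silent at 12 months, months 0–3 kept | 91.0% |
| 10% contribute nothing | 89.9% |

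The plan's 10% allowance covers this.

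**3. Events unobserved.** Average planning rate (2.25 + 1.80)/2 = 2.025 per year. At an assumed 10% non-response at 12 months: 804 × 0.10 × 2.025 × 0.75 ≈ 122 events in months 3–12. At an assumed 20%: about 244.

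**4. Bias in the rate ratio (all inputs assumed).** Let p be the share lost and g their event rate relative to those retained, with subscript 0 for control and 1 for BCG. If lost participants contribute nothing, observed ratio = true ratio × [(1 − p0) + p0·g0] / [(1 − p1) + p1·g1].

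- p = 10% and g = 1.5 in both arms: factor 1.00, no bias.
- p = 15% control, 5% BCG, g = 1.5 in both: 1.075/1.025 = 1.049, so a true 0.80 appears as 0.84.
- p = 10% in both, g = 1.5 in BCG only: 1/1.05 = 0.952, so 0.80 appears as 0.76.
- The same BCG-only case with months 0–3 kept, by simple person-time: observed BCG rate (0.9 + 0.025 × 1.5)/0.925 = 1.0135 against a true 1.05; 1.0135/1.05 = 0.965, so 0.80 appears as 0.77.

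**5. Look-back.** With both contacts on time, 3 months from baseline and 9 months back from month 12 meet exactly. A gap opens in two cases:

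- *Window edges (section 9.8).* A 3-month contact at −14 days falls at about month 2.5. A 12-month visit at +1 month looks back to month 4. The gap is about 1.5 months; the opposite extremes give a similar overlap.
- *Missing 3-month form.* The amber band in section 8.1 tolerates 10–20% missing: 804 × 0.10 × 2.025 × 0.25 ≈ 41 events, or about 81 at 20%, in months 0–3 that the exacerbation item does not ask about.

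The 12-month prescription and hospitalisation items and the event-level exacerbation forms fill part of this, but the first two need a 12-month response.

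**The case against.** The strongest reply is that nothing forbids record retrieval. The missing-data wording in sections 9.6 and 9.7 can be read as governing unreturned forms only. Section 14.2.5 promises every attempt at full data, section 18.7 has the committee review medical history for each participant every three months, and section 11.3 allows remote record access for treatment data. This stands in part: a reader might infer that these events are bound to be lost, and the text does not say that. But the checks in sections 8.1 and 11.3 start from something the patient has reported, and the committee sees what the trial office supplies. No section tells anyone to search the record of a silent participant, and section 9.7 points the other way.

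Three further inferences go too far:

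- *Months 0–3 are never asked about.* The two forms are designed to join, and the 12-month visit asks for prescriptions and admissions over 12 months. The gap is conditional and partial.
- *The imputation only repeats the primary model for people with no data.* Section 14.2.5 also lists previous responses as inputs and leaves the details to the SAP, so its adequacy cannot be judged here.
- *The result will favour BCG by 5%.* That is one assumed scenario. It shrinks to about 3.5% if months 0–3 are kept, vanishes under equal and similarly informative loss, and reverses if more controls are lost.

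**Conclusion.** The point holds as a mismatch the protocol itself fixes: an outcome defined by the record is treated as missing when a participant does not reply, and a treatment-policy label is attached to events that section 14.2.5 handles by censoring. At an assumed 10% non-response at 12 months, about 122 events go unobserved. The consequence is possible bias of a few per cent in the rate ratio, of unknown direction and resting wholly on assumed differences in loss or event rates between arms. Power does not carry the argument, since the loss is budgeted (about 90% at 361 per group, about 92.7% at 402). The 9-month look-back is a secondary weakness, not an error in itself. The change is worth making because it is cheap and reduces reliance on an assumption the trial need not make.

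**What to change.** 1. **Sections 9.6, 9.7 and 14.2.5.** For every participant who has not chosen the section 9.9 category that ends all further data collection, the site reviews the record for AECOPD prescriptions and admissions over the full 12-month outcome window and sends them to the adjudication committee. Confine missing to questionnaire items such as CAT.
2. **Section 9.7.** Run the 12-month exacerbation look-back to the start of the outcome window (vaccination, or randomisation if no vaccine was given) or to the last completed form.
3. **Section 14.2.1.** Stop labelling loss to follow-up and refusal of data collection as treatment-policy intercurrent events, treat them as missing data, and state that exposure ends at death.

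Cost: record look-ups for about 80 participants (10% of 804) at sites that already confirm events from records, one form change and some protocol text. The required sample size does not change. Events found only in the record will lack the patient symptom form and samples, so the committee will have less to judge them on, especially for aetiology. Participants who refuse all data collection remain unrecoverable.

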9.8 Schedule of assessments

Event	Baseline	IGRA test	Vaccine administered ¹	1 month +/-7 days ²	3 months +/- 14 days ²	12 months +/- 1 month ²
Eligibility check	X					
Consent	X					
IGRA test	X	X ³				
Demographics	X					
Medical history (including vaccine history)	x					х
Smoking status	X					Х
Medications	X					Х
Spirometry (FEV1/FVC)	X					
CAT score	X				X	Х
Randomisation	X					
IGRA test results		Х				
Pregnancy test (if applicable)			x			
BCG			X			
Exacerbation rate/symptoms/treatment	x				X	х
DBS (all participants)	X				X	Х
Sputum sample	X				Х	
Throat/nose swab	X				Х	
DBS (exacerbation sampling)					Х	

Table 2: Schedule of Assessments

STABILISE Protocol

Venepuncture	Х		X4	X4	X ⁴
Follow up questionnaire				Х	X
Adverse events				Х	Х

¹ The vaccine, where allocated, should be administered to the participant within 6 weeks of randomisation.

²Follow up dates will be calculated using the date that the treatment was administered on for those allocated to the intervention arm and the date of randomisation for those allocated to the control arm.

³Further test required if result of first test is indeterminate

⁴*Mechanistic subgroup only*

9.9 Withdrawal and changes in levels of participation

Informed consent is defined as the process of learning the key facts about a clinical trial before deciding whether or not to participate. It is a continuous and dynamic process, and participants should be asked about their ongoing willingness to continue participation at all visits. Participants should be aware from the beginning that they can freely withdraw (cease to participate) from the trial at any time. A participant may wish to cease to participate in a *particular* aspect of the trial. Participants found to be ineligible post randomisation, for reasons other than to a positive or two indeterminate IGRA results, should be followed up according to all trial processes and will still have their data analysed unless they explicitly change their level of participation. Participants found to be ineligible post randomisation due to a positive or two indeterminate IGRA results will not be followed up and we will not collect any further data.

The changes in levels of participation within the trial are categorised in the following ways:

No trial intervention: The participant would no longer like to receive the trial intervention but is willing to be followed up in accordance with the schedule of assessments and if applicable using any central UK NHS bodies for long-term outcomes (i.e., the participant has agreed that data can be collected and used in the trial analysis).

No trial related follow-up: The participant does not wish to attend trial visits and/or undertake assessments in accordance with the schedule of assessments, but is willing to be followed up at standard clinic visits and if applicable using any central UK NHS bodies for long-term outcomes (i.e., the participant has agreed that data can be collected at standard clinic visits and used in the trial analysis, including data collected as part of long-term outcomes).

No further data collection: The participant is not willing to be followed up in any way for the purposes of the trial AND does not wish for any further data to be collected (i.e., only data collected prior to any changes of levels in participation can be used in the trial analysis).

The details of changes of levels in participation within trial (date, reason and category of status change) should be clearly documented in the source documents.

10. ADVERSE EVENT REPORTING

10.1 Definitions

Table 3: Adverse event reporting definitions

Severity Definitions	Mild Moderate Severe	Awareness of signs or symptoms that do not interfere with the participant's usual activity or are transient and resolved without treatment and with no sequelae. A sign or symptom, which interferes with the participant's usual activity. Incapacity with inability to do work or perform usual activities.
Adverse Event	AE	Any untoward medical occurrence in a participant administered a medicinal product and which does not necessarily have a causal relationship with this intervention. An AE can therefore be any unfavourable and unintended sign (including abnormal laboratory findings), symptom or disease temporally associated with the use of an investigational medicinal product, whether or not related to the investigational medicinal product.
Adverse Reaction	AR	All untoward and unintended responses to an IMP related to any dose administered. An AE judged by either the reporting Investigator or Sponsor as having causal relationship to the IMP qualifies as an AR. The expression reasonable causal relationship means to convey in general that there is evidence or argument to suggest a causal relationship.
Serious Adverse Event	SAE	Any untoward medical occurrence or effect that: Results in death Is life-threatening* Requires hospitalisation or prolongation of existing hospitalisation Results in persistent or significant disability or incapacity Is a congenital anomaly/birth defect Or is otherwise considered medically significant by the Investigator**
Serious Adverse Reaction	SAR	An AR which also meets the definition of a SAE.
Unexpected Adverse Reaction	UAR	An AR, the nature or severity of which is not consistent with the applicable product information (e.g., Investigator Brochure for an unapproved IMP or (compendium of) Summary of Product Characteristics (SPC) for a licensed product).

		When the outcome of an AR is not consistent with the applicable product information the AR should be considered unexpected.
Suspected Unexpected Serious	SUSAR	A SAR that is unexpected i.e., the nature, or severity of
Adverse Reaction		the event is not consistent with the applicable product information. A SUSAR should meet the definition of an AR, UAR and SAR.

* The term life-threatening is defined as diseases or conditions where the likelihood of death is high unless the course of the disease is interrupted.

** Medical events that may not be immediately life-threatening or result in death or hospitalisation but may jeopardise the participant or may require intervention to prevent one of the other outcomes listed in the definitions above.

